In addition to unadjusted analyses, we will also perform multiple regression to adjust for a priori-selected risk factors for outcomes, including age, severity of illness, admission diagnosis of sepsis, and duration of coma prior to randomization. Adjusting for strong risk factors of outcome variables is known to reduce measurement error, which may increase statistical power. 247 We will carefully assess differential effects of antipsychotic treatment by study sites by examining site-specific effects as well as by a formal interaction analysis using multiple regression. We will include study site as a random effect. For the analysis of delirium/coma-free days and other continuous outcomes, we will choose the type of multiple regression by carefully examining the distribution of the data. Cox proportional hazards regression  will be used to analyze the adjusted effect of antipsychotic treatment on time-to-event outcomes (including oneyear survival), with censoring as appropriate. The proportionality assumption for Cox regression will be assessed graphically, using log-minus-log survival plot, and by adding interaction terms between each covariate and time in the model. The number of variables to be included in each regression analysis will be based on the rule of thumb that a multivariable regression model must include no more than m/10 parameters for it to be reliable on future similar patients, where m is the effective samples size (e.g., number events for Cox regression or number of patients for

MIND-USA Protocol Version: 1.15 Confidential Protocol Date: June 22, 2016 35 of 51

proportional odds logistic regression). This approach avoids overfitting and ensures robustness of regression parameters.

In addition to assessing whether study site modifies the effects of antipsychotic treatment on outcomes, as described above, we will also assess whether patient characteristics modify the effects of the interventions on outcomes to identify a subcategory of patients who may benefit more than others. For these analyses, we will develop multiple regression models that include interaction terms between study group and clinical characteristics, such as age, sepsis, and duration of coma prior to randomization. Nonlinearity of the association between continuous variables and outcomes will be assessed by inclusion of restricted cubic splines.

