- 3. Upon completion of in-hospital data cleaning, the REDCap database **MIND-USA Study: In-Hospital Database** will be locked in the following way:
 - a. Initially all study site personnel will be restricted to "read-only" user access for the entire database. VCC Project Managers and the Follow-Up Team will be restricted to read-only access for all fields except those needed for patient contact, reconsenting, DNA permissions, notes to file and event reporting, and tracking dates of death and study withdrawal. All fields not needed by these teams will be restricted to read only by use of the @readonly action tags. The follow-up team will continue to be blinded (via restricted access) to all information about the hospital course, as has been the case throughout the study.

	VCC Project Managers	Follow-Up Team
Dates Tracking Form - all variables made read-only (using action tag @readonly) to all users except variables pertaining to consenting, death and study withdrawal	View and Edit	View and Edit
Contact Form - all fields	Read Only	View and Edit
NTF - all fields	View and Edit	View and Edit
Adverse Events - all fields	View and Edit	View and Edit
DNA Log - all fields	View and Edit	No Access
All other forms/fields	Read Only	No Access

- b. During the remaining Follow-Up period, the sites will be given a window for downloading their data for local storage.
- c. Once 12-month follow-up is completed, we will conduct final data cleans on the updated information and then permanently move the entire database to inactive status, meaning that no data can be changed unless serious errors are noted.

A log of all steps in this process will be maintained in the Database Cleaning & Lock SOP.

4. Statistical Principles

Statistical analysis will be conducted in accordance to the plan outlined in this SAP. Statistical analysis will abide by these general statistical principles below.

Confidence Intervals and P-Values

Level of statistical significance will be set at 5% (with multiple comparisons adjustments for the primary outcome, as noted below). All tests will be two-sided. 95% confidence intervals will be reported along with all effect estimates. Presentation of results will emphasize clinical significance, effect sizes and confidence intervals, over statistical significance.

Modeling Principles

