Whenever possible (based on variable distribution), we will not assume linear associations between covariates and outcomes; rather, nonlinear associations between continuous variables and outcomes will be permitted by inclusion of restricted cubic splines with 3 knots. To account for correlation among patients within a given site, we will adjust standard errors using Huber-White sandwich estimation.

Multiple Comparisons

For the primary outcome (DCFDs), multiple comparisons will be conducted at a 2.5% level if the overall test of association is significant at a 5% level. Regarding the analyses of all *a priori*-defined secondary outcomes described herein, no adjustments will be made for multiple comparisons, in keeping with authoritative recommendations on this topic and standard practice when analyzing multiple, prospectively defined outcomes in a clinical trial. As described in our proposal, each comparison made will be hypothesis-driven and based upon biological plausibility rather than hypothesis-generating in nature.

Missing Data

Individual Variables

Missing data for individual variables will be imputed using clinical imputation rules when appropriate; details on these rules are noted in the Definitions and Derived Variables section. This section also describes the imputation process for summary variables for mental status (eg, days alive and free of delirium and coma), which may involve *partially* missing data.

Missingness when Modeling

In adjusted analyses, model-based multiple imputation strategies will be used (using R's mice library) if >5% of any covariates are missing. In all cases, decisions and processes will be documented both in data management and analysis code and in statistical reports.

Adherence to the Intervention and Protocol Noncompliance

Definition & assessment of adherence to the intervention

All analysis will be conducted based on the intention to treat principle. Subjects will be considered to have the treatment they were randomized to regardless of withdrawal from treatment or extent of exposure.

Presentation of adherence to intervention

We will describe, within each treatment group, the following:

- Patient level:
 - How many randomized patients received >=1 dose of study treatment
 - Days each randomized patient received study treatment
 - Doses of study treatment each randomized patient received, along with average daily dose

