All in-hospital outcomes will be analyzed using both univariate methods and multivariable regression, adjusting for covariates noted below. Though patient characteristics should theoretically be balanced between treatment groups due to randomization, adjustment increases our power and precision. Though we will perform both types of analyses for each outcome, adjusted analyses will be considered the primary analysis.

Unadjusted Analyses

In-Hospital Continuous Outcomes

We will analyze continuous outcomes (delirium/coma-free days [PO]; delirium duration [total, SO2; hyperactive and hypoactive delirium separately; coma duration; mean CV SOFA and lowest mean arterial pressure]) using the Kruskal-Wallis test. These outcomes are typically not normally distributed; therefore, the assumptions for a parametric ANOVA would be violated, and results would be unreliable. The nonparametric Kruskal-Wallis test does not assume that the outcome has a normal distribution, and thus provides more power and reliability in the case of a non-normal distribution.

If the unadjusted test for the primary outcome (DCFDs) only is statistically significant, we will use Dunn's test for pairwise differences between treatment groups, using a Bonferroni correction for multiple comparisons at a 2.5% alpha level.

Time to Event Outcomes

We will describe and test for differences in time to death (**SO1**) using Kaplan-Meier curves and the log-rank test, respectively. ICU and hospital discharge, liberation from mechanical ventilation, and ICU readmission all have a competing risk of death (**SO3**, **SO4**, **SO5**, and **SO6**, respectively). (For ICU readmission and liberation from mechanical ventilation, hospital discharge without experiencing the outcome will be treated as an additional competing risk.) Therefore, we will describe the cumulative incidences of both the outcome of interest and each competing risk, along with a modified chi-squared test for the difference between groups in the subdistribution of interest (Gray 1988). Patients who withdrew in the hospital with no discharge or death information available are censored at the time of withdrawal; we censor at x.01 days anyone who has experienced neither death nor the outcome of interest by x days (where x is the end of the time frame specified above for each outcome). We will detail how many and when patients were censored for each analysis.

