"Time 0" will be the time of randomization for each of these outcomes, with the exception of ICU readmission; for this outcome, "time 0" will be the time of the first ICU discharge, and only patients who survived their first ICU admission will be included.

Long-Term Outcomes

We will use multivariable regression to analyze the relationship between treatment group and scores measuring long-term neuropsychological, quality of life, and PTSD outcomes as outlined in the Outcomes section above. Depending on the distribution of each outcome, we will use linear regression, negative binomial regression, or proportional odds logistic regression, as appropriate. These models will not include covariates other than treatment.

For each outcome, we will have separate models for 3- and 12-month scores. At each time point, we include all patients with available outcome data, using inverse probability weighting to account for patient death and attrition. To decrease reliance on a few highly influential observations, we will truncate weights at the top 1 percentile.

As a sensitivity analysis, we will also define long-term outcomes using the unadjusted composite endpoint approach (reference: Lachin) to deal with outcomes truncated due to death or loss to follow up. The composite endpoint will be defined as:

- If the patient dies prior to assessment: days between randomization and death
- If the patient survives and is successfully assessed: days between randomization and planned assessment (constant) + assessment score

For example, if we are analyzing a 3-month outcome, the constant would be 90. Differences between the composite end point distribution amongst groups will be assessed using the Kruskal-Wallis test.

Adjusted Analyses

We will adjust all coefficient variances using Huber-White sandwich estimation, clustered by study site. This will help account for unmeasured variability and correlation among patients within a given site.

In-Hospital Continuous Outcomes

We will use proportional odds logistic regression for continuous outcomes (delirium/coma-free days; delirium duration [any, hyperactive, and hypoactive]; coma duration; mean CV SOFA and lowest mean arterial pressure); this method assumes an ordinal outcome but does not assume that it follows a specific statistical distribution.

If the overall test for treatment vs our primary outcome (DCFDs) is significant at the 5% level, we will report individual treatment tests vs placebo at the 2.5% level.

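### The primary DCFD analysis clusters its sandwich variance by site but names no small-cluster correction, reference distribution or test type, so its error rate is not controlled if sites are few

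*SAP*

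**What the plan says.** SAP section 7 (Analysis Methods) reports each in-hospital outcome unadjusted and adjusted, and settles which one counts: "adjusted analyses will be considered the primary analysis". For DCFDs the adjusted model is proportional-odds logistic regression. Under Adjusted Analyses the variance rule is "We will adjust all coefficient variances using Huber-White sandwich estimation, clustered by study site". Section 4 (Modeling Principles) gives the same rule: "To account for correlation among patients within a given site, we will adjust standard errors using Huber-White sandwich estimation".

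The decision procedure is in section 4 (Multiple Comparisons): "multiple comparisons will be conducted at a 2.5% level if the overall test of association is significant at a 5% level". Section 7 repeats it for the adjusted model: "we will report individual treatment tests vs placebo at the 2.5% level". Section 4 also says: "Presentation of results will emphasize clinical significance, effect sizes and confidence intervals, over statistical significance".

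No section says whether the overall test is Wald, score or likelihood-ratio, which reference distribution applies, or whether the sandwich is corrected for a limited number of sites. Section 9 leaves only package versions to the analysis report.

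Protocol 11.4 handles site differently. It says "We will include study site as a random effect", and plans to study differences in treatment effect between sites with "a formal interaction analysis using multiple regression". In the SAP, site is in neither the covariate list nor the effect-modification list, although it is a randomisation stratum (Protocol 6.2, SAP 3.2).

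**The concern.** A variance clustered by site takes the site, not the patient, as the independent unit. Its precision therefore depends on the number of sites, G, and not on the 561 patients. With few sites the uncorrected sandwich is biased downwards and noisy, while chi-square and normal cutoffs treat it as known. The test is then liberal even when outcomes do not differ between sites at all.

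The 5% gate, the 2.5% tests against placebo and the 95% intervals for the primary endpoint are at stake. The intervals matter most for presentation, because the SAP puts them ahead of significance and they have no gate.

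**Working it through.** **Inputs from the documents.** 187 per arm, N = 561; control DCFDs 6.8 ± 5.2; 2-day difference; two-sided 2.5% per comparison (SAP 3.3, Protocol 11.1). Three arms 1:1:1 within site-by-age strata (SAP 3.2), in blocks of 6 and 8 (Protocol 6.2). Six covariates (SAP section 7), with 3-knot splines (SAP section 4).

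**Assumed.** G = 10 to 40; site sizes from equal to a coefficient of variation (CV) of 0.7; a robust Wald overall test with chi-square(2) cutoff 5.99 and normal cutoffs for pairwise tests and intervals.

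**The plan's own figure.** 2 / (5.2 × √(2/187)) = 3.72; 3.72 − 2.24 = 1.48, so power is 93%, against 92% stated. The calculation treats patients as independent and makes no allowance for estimating a variance from G sites.

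**Closed form, equal sites.** The treatment estimate behaves like a mean of G independent two-component site contributions. The uncorrected sandwich divides by G rather than G − 1, so the Wald statistic is G/(G−1) times a Hotelling statistic:

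W ~ [2G/(G−2)] × F(2, G−2), so P(W > 5.99) = (1 + 5.99/G)^(−(G−2)/2).

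For G = 10: (1.599)^(−4) = 15.3%. Interval coverage is P(|t(G−1)| < 1.96 × √((G−1)/G)); for G = 10 the limit is 1.859 on 9 df, which gives 90.4%.

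**Simulation under the null.** Proportional-odds fit with two treatment terms and 12 covariate columns; 15-level outcome matched to 6.8 ± 5.2; site SD 0.3 log-odds; blocks of 6 and 8. A block of 8 cannot be split 1:1:1, so it was drawn 3/3/2 with a random short arm (assumption). There were 7,400 null trials per scenario at 10-20 sites and 5,000 at 30-40, with a Monte Carlo error of about 0.2-0.5 points. Gated means overall p < 0.05 and at least one pairwise p < 0.025. Ranges run from equal sites to CV 0.7.

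| Sites | Closed form, overall | Simulated, overall | Simulated, gated | Closed-form coverage | Simulated coverage |
|---|---|---|---|---|---|
| 10 | 15.3% | 15.7-19.1% | 10.3-12.8% | 90.4% | 88.5-90.0% |
| 16 | 10.8% | 10.4-13.8% | 7.3-9.3% | 92.3% | 90.7-92.1% |
| 20 | 9.5% | 9.4-11.3% | 6.2-7.5% | 92.9% | 92.0-93.0% |
| 30 | 7.8% | 7.2-7.9% | 5.0-5.7% | 93.6% | not run |
| 40 | 7.1% | 6.8-8.3% | 4.5-5.8% | 94.0% | not run |

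Model-based variance on the same data gave 4.5-5.5% overall and 3.1-4.0% gated. The benchmark for the gated claim is therefore 3-4%, not 5%.

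**Sensitivity.**
- No site effect (16 sites, CV 0.7): 12.6% overall, 9.0% gated. The excess does not come from site differences.
- A separately written simulation with blocks of 6 and 9 gave 9.4-19.1% overall and 6.8-12.2% gated at 10-20 sites, and 6.6-8.2% and 4.8-5.9% at 30-40.
- At CV 1.0 that simulation gave 23.8%, 15.5%, 13.0%, 10.0% and 8.2% overall at 10, 16, 20, 30 and 40 sites. Very uneven sites would exceed the ranges in the table.

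**The case against.** The strongest reply is that the size rests on three things the text does not state: the number of sites, the cutoffs and the form of the overall test. This stands, and it makes every figure conditional. The SAP attaches the sandwich to coefficient variances and standard errors and never calls the overall test a Wald test. A likelihood-ratio gate should hold close to 5%, and the gated claim cannot exceed its gate. The excess in that claim would then largely go. The intervals would still be too narrow.

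The analysis code may already apply a correction. If so, one sentence in the SAP closes that part.

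Kruskal-Wallis with Dunn's test does not use this variance and would be read beside the adjusted result. It is a partial check, but the SAP does not make it primary.

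Two stronger readings are tempting.
- A reader might infer that the trial's type I error is 9-19%. The documents do not support that. The only centre count in the text is the pilot's six, title and contact pages are missing from the text reviewed, and at 30-40 sites the gated claim is near 5%.
- A reader might take the threshold of 30 randomised patients in Protocol 9.4 as evidence of large, uneven sites. It is only a monitoring sample rule (three records, or 10% above 30; 10% of 30 is three) and forecasts no site's accrual.

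The difference between protocol and SAP on site is a separate inconsistency, not evidence of inflation. The protocol's random-effect sentence follows directly on its site-interaction sentence, so its scope can be argued.

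**Conclusion.** The point holds in conditional form and should be fixed. As written, the primary test and its intervals are not fully specified, and the named estimator without a correction is liberal when sites are few. With a robust Wald test and chi-square/normal cutoffs, an assumed 10-20 sites and size CV up to 0.7, the true size is about 9-19% overall and 6-13% gated (3-4% with a valid variance), with interval coverage of about 88-93%. At an assumed 30-40 sites it is about 7-8% and 4.5-6%, which is modest. Confidence is medium, because the site count decides the weight. Whatever that count is, the SAP's departure from Protocol 11.4 on site needs reconciling.

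**What to change.** Amend SAP sections 4 and 7 before unblinding, which SAP 3.2 still places in the future. State the type of overall test, and choose one of these.

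(a) Preferred: include site in the primary proportional-odds model, as Protocol 11.4 states, with model-based variance, and restore the treatment-by-site interaction check. A separate linear-model simulation with site in the model and model-based variance gave about 5% overall; a random site intercept in the proportional-odds model was not simulated. Say in the SAP that model-based standard errors do not allow for treatment effects that differ by site. With an assumed SD of 0.3 log-odds per arm (16 sites, CV 0.7), model-based variance, without a site term in that run, rejected an average-effect null 12.6% of the time.

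(b) Otherwise keep site clustering and prespecify a single small-cluster method: the delete-one-site jackknife (CR3) with factor (G−1)/G, F(2, G−2) for the overall test, and t(G−1) for the pairwise tests and intervals. At 10-20 sites this gave 5.0-7.5% overall and 3.1-4.3% gated. It is not exact, so check its size for the real site sizes by assigning sham treatment labels within site-by-age strata on the blinded data. A bare G/(G−1) factor with chi-square cutoffs is not enough: it left 8.5-16.8% overall at 10-20 sites.

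In either case, reconcile SAP sections 4 and 7 with Protocol 11.4.

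Cost: wording and a few lines of code, with no new data. Option (b) loses power when sites are few. For a 2-day benefit of one drug (CV 0.7), gated power is 81.2%, 88.5% and 89.7% at 10, 16 and 20 sites, against about 95% for the uncorrected test, which does not hold its level.

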#### 6.0 Enrollment/Randomization

- **6.1.** Screening and Obtaining Informed Consent (Pre-Randomization Phase). Study personnel at each site will screen every day using the ICU census. When an eligible patient is identified (i.e., inclusion criteria are met and no exclusion criteria are present), informed consent will be pursued; when obtained, the patient will be included in the Pre-Randomization Phase of the study, which will include approximately 1,300 participants. Surrogate consent will be required for most patients because during the initial phase of their illness they will often be either comatose or delirious. However, all patients consented via surrogate will be re-consented for participation in the trial once competent. 177,178
- **6.2. Randomization (Interventional Trial Phase)**. Once informed consent is obtained, patients will be assessed twice daily for delirium using the CAM-ICU. When a patient becomes delirious (i.e., CAM-ICU positive), they will advance to the Interventional Trial Phase of the study and be assigned via randomization to one of the three treatment groups. Based on the most recent screening data from participating sites, we estimate 50%-60% of approximately 1,100 patients included in the pre-randomization phase will develop delirium, often after a short period of coma. We will thus be able to randomize 561 or more patients to participate in the Interventional Trial Phase, meeting our calculated sample size (see Section 11.1).

Randomization will be conducted in a 1:1:1 ratio to treatment with haloperidol, ziprasidone, or placebo using a computer-generated randomization scheme (with permuted block sizes of 6 and 8) stratified by study center and age (< 70 years vs.  $\ge 70$  years). The randomization scheme will be created by the study's primary biostatistician and will be distributed directly to the investigational pharmacy at each study site as a set of randomization lists stratified by study center and age (< 70 years vs.  $\ge 70$  years). Once a consented patient has become delirious and an order for blinded study drug is placed, the investigational pharmacist will refer to the appropriate randomization list (determined by the patient's age) to establish that patient's treatment assignment. The lists will only be accessible to investigational pharmacists, so that treatment assignment will be known only by the investigational pharmacists.

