Time to Event Outcomes

We will use Cox proportional hazards regression for mortality. For all other time to event outcomes (ICU and hospital discharge, ICU readmission, and liberation from mechanical ventilation), we use Fine-Gray competing risks regression, treating death as our competing risk. (For ICU readmission and liberation from mechanical ventilation, hospital discharge without experiencing the outcome will be treated as an additional competing risk.) Patients who withdrew in the hospital with no discharge or death information available will be censored at the time of withdrawal; we will censor at x.01 days anyone who has experienced neither death nor the outcome of interest by x days, where x is the end of the time frame specified above for each outcome. Details on censoring will be provided with each analysis.

"Time 0" will be the time of randomization for each of these outcomes, with the exception of ICU readmission; for this outcome, "time 0" will be the time of the first ICU discharge, and only patients who survived their first ICU admission will be included.

Long-Term Outcomes

We will use the same modeling techniques as described in "Unadjusted Analyses" above; however, here, we will adjust for the covariates listed below.

Model Assumptions

Model assumptions will be evaluated graphically. Proportional odds assumptions will be checked using logistic regression with multiple cutoffs for proportional odds assumption (see Harrell's *Regression Modeling Strategies*, section 13.3.3) and Schoenfeld residuals will be used for proportional hazards. If linear regression is used for long-term outcomes, we check residual vs fitted plots and quantile-quantile plots to ensure assumptions are met. For negative binomial models, we will check goodness-of-fit measures.

Covariates

Covariates for all multivariable regression models include (all demographic or ICU admission characteristics):

- Age at study consent
- Preexisting CI, via the IQCODE (performed via patient or surrogate questionnaire)
- Preexisting frailty, via the CSHA Clinical Frailty Score
- Preexisting comorbidities, via the Charlson Comorbidities Index
- SOFA on the day of randomization, excluding the CNS component
- Level of arousal at randomization, via the RASS closest to the time of randomization

Prior to modeling, we perform redundancy analyses to ensure that no covariates completely explain any of the others (resulting in multicollinearity).

Exploratory Analysis

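### The SAP's primary adjusted model leaves out admission sepsis, pre-randomisation coma duration and a site term in the mean model, all named in Protocol 11.4, and gives no reason.

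*SAP*

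**What the plan says.** **Protocol 11.4** commits the regression analyses to "a priori-selected risk factors for outcomes, including age, severity of illness, admission diagnosis of sepsis, and duration of coma prior to randomization". On site it says "We will include study site as a random effect", and "We will carefully assess differential effects of antipsychotic treatment by study sites" through site-specific estimates and a formal interaction. It also gives duration of coma before randomisation as an example of an effect modifier. Randomisation is "stratified by study center and age" (Protocol 6.2; SAP 3.2 agrees).

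**SAP section 7** states that "adjusted analyses will be considered the primary analysis". Its Covariates subsection opens "Covariates for all multivariable regression models include (all demographic or ICU admission characteristics") and lists six: age, IQCODE, frailty, Charlson index, "SOFA on the day of randomization, excluding the CNS component", and the RASS nearest randomisation. Site enters only through Huber-White variances clustered by site (section 4, Modeling Principles, and section 7, Adjusted Analyses). The effect-modification models use age, severe sepsis at ICU admission, IQCODE, and medical versus surgical status. Coma duration before randomisation appears nowhere in the SAP, and neither does a treatment-by-site analysis. No reason is given for any of these changes.

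**The concern.** The primary outcome counts days free of delirium and coma. How long a patient was comatose before entry is a natural predictor of that count, and the protocol treated it as one. A SAP that promotes the adjusted model to primary and then drops two covariates named in advance raises two questions.

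- **Efficiency.** The SAP's own reason for adjusting is power and precision. Omitting prognostic terms gives some of that back. In a proportional odds model, the odds ratio is also conditional on the covariate set, so changing the list changes the quantity reported.
- **Traceability.** A reader who compares the two documents finds a different model and no explanation.

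Site is a related case. It is a randomisation stratum, but it is missing from the linear predictor, and the planned look at whether the treatment effect varies by site has gone.

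**Working it through.** **1. The two lists side by side**

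| Item | Protocol 11.4 | SAP section 7 |
|---|---|---|
| Age | covariate | covariate |
| Severity of illness | covariate | non-CNS SOFA, day of randomisation |
| Admission sepsis | covariate, modifier | modifier model only |
| Coma duration before randomisation | covariate, modifier | absent |
| Site | random effect | clustered variance only |
| Treatment by site | formal interaction | absent |
| IQCODE, frailty, Charlson, RASS | not named | covariates |

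**2. The plan's own power figure**

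Inputs (Protocol 11.1, SAP 3.3): 187 per arm, difference 2 days, SD 5.2, two-sided alpha 2.5%, stated power 92%.

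- Standard error = 5.2 × √(2/187) = 0.538
- 2 / 0.538 = 3.719; the critical value is 2.241
- Power = Φ(3.719 − 2.241) = Φ(1.478) = 93.0%

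The noncentral t gives 92.9%. A Wilcoxon efficiency of 0.955 gives 91.8%. The stated 92% is reproduced. It assumes no covariate adjustment, so the changed list does not undermine it.

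**3. What the omitted terms could add**

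The documents give no R² for sepsis or coma duration, so a range is assumed. By linear approximation, residual SD = 5.2 × √(1 − R²), and power = Φ(3.719/√(1 − R²) − 2.241).

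| Assumed added R² | Power | Difference detectable at 80% power |
|---|---|---|
| 0 | 93.0% | 1.66 days |
| 1% | 93.3% | 1.65 days |
| 2% | 93.5% | 1.64 days |
| 5% | 94.2% | 1.62 days |
| 10% | 95.3% | 1.57 days |

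From the unrounded powers (93.02% to 93.27% and to 95.34%), the gain is about 0.2 to 2.3 points. If the SAP's six covariates already explain 10%, the starting point is 95.3%, and a further partial R² of 1% to 10% gives 95.5% to 97.1%.

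**4. Does this carry over to the planned model?**

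The primary model is proportional odds, where adjustment acts differently. In a simulation with 187 per arm and a covariate explaining 6% to 10% of latent variance, the standard error of the log odds ratio was about 0.4% to 0.6% larger with adjustment. The test statistic was about 3% to 5% larger, because the odds ratio moved away from 1. The linear factor 1/√(1 − R²) is 1.03 at 6% and 1.05 at 10%, so the linear power gain is a fair guide even though its mechanism is not.

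**5. Is there room in the model?**

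Protocol 11.4 allows m/10 parameters; for the primary outcome, 561/10 = 56. The SAP model uses at most about 2 + 6 × 2 = 14 (treatment, plus two spline degrees of freedom per covariate). Sepsis (1) and coma duration (2) bring it to 17, and a site random intercept adds one variance parameter. Overfitting does not explain the omission. In the Cox models the limit is set by deaths. With the 31% mortality expected in Protocol 11.3, 561 × 0.31 = 174 deaths, so the limit is about 17 at one year and lower at earlier time points.

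**6. Do the SAP's covariates stand in for coma duration?**

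Only weakly. Patients are randomised when CAM-ICU positive (Protocol 6.2), and SAP section 8 classes RASS −4 or −5 as coma. The RASS nearest randomisation will therefore usually be −3 or above, whether or not the patient has just spent days in coma. The SOFA covariate leaves out its CNS component.

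**The case against.** The strongest reply is that the SAP exchanged covariates. Protocol 11.4 introduces its list with a word that leaves it open. The SAP keeps age and severity and adds four baseline measures. SOFA on the day of randomisation takes up part of what sepsis would carry, and sepsis is still modelled as a modifier. Nothing in the documents shows that the SAP's set is less prognostic than the protocol's. This stands as an argument against calling the change a serious loss. It does not supply the missing reason, and it covers coma duration poorly.

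Four stronger readings are tempting, and the documents do not support them.

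- **Site has been ignored.** It has not: clustered variances address within-site correlation. What is lost is site in the mean model and the site interaction. Because treatment is randomised within site, the expected gain from the former is small. The text reviewed does not give the number of sites, so small-cluster behaviour of the sandwich estimator cannot be judged.
- **The standard error would shrink by the linear-model factor.** The primary model is proportional odds, where the simulation shows a slightly larger standard error.
- **The unadjusted tests should be stratified by site.** Protocol 11.4 itself specifies unstratified Kruskal-Wallis and log-rank tests, and these are not the primary analysis.
- **All the protocol's variables are on file.** Sepsis and site are. RASS is recorded twice daily only from consent (Protocol 7.2). Consent may follow eligibility by up to 72 hours, or 120 hours in persistent coma (Protocol 5.2), and SAP section 8 notes that study data before consent can be missing.

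**Conclusion.** The point holds as an unexplained protocol-SAP discrepancy in the primary model, with a modest efficiency cost. Two covariates named a priori are absent, site is not in the mean model, and two planned interactions have disappeared.

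The power at stake is about 0.2 to 2.3 points from a base of 93%. That rests on an assumed added R² of 1% to 10%, which must be over and above the six SAP covariates, and on a linear approximation.

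A reader might infer that the primary test is invalid or biased. It is not: under randomisation, leaving out baseline covariates keeps the test of no effect valid, and the odds ratio from a shorter list is conditional on a different set, which is not bias. A reader might also infer that covariates were chosen to suit the result. The documents do not show that. SAP 3.2 places unblinding after data cleaning, and section 8 describes its missing-data counts as taken before unblinding. A dated reason would close the question.

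**What to change.** Before unblinding, amend SAP section 7 as follows.

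1. Add severe sepsis at ICU admission (yes/no) to the in-hospital adjusted models. It is already a SAP variable, and it fits the list's own description as an admission characteristic better than SOFA and RASS taken at randomisation do.
2. Add observed coma days between consent and randomisation, labelled as a partial measure because earlier coma may be unrecorded.
3. Include study site in the mean model as a random intercept, as Protocol 11.4 states.
4. Restore the treatment-by-site and treatment-by-coma-duration checks.
5. For any item the sponsor prefers not to restore, record a dated reason and bring Protocol 11.4 into line.

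The cost is SAP wording, a few lines of code and three extra degrees of freedom plus a site variance, on 561 patients. The coma variable will be noisy: patients already delirious at consent would score zero whatever their earlier course. In the Cox models for death, where the m/10 limit is tight, enter the added and existing terms with fewer spline degrees of freedom.
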